## 4.3.2 Patient Replacement Policy

Patients withdrawn from the study after having started treatment with the IMP will not be replaced, if they have received more than 50 exposures with the IMP. Patients with less than 50 EDs need to be replaced.

## 4.4 Assignment of Patients to Treatment Groups

As this is a single-arm study, assignment of patients to treatment groups is not necessary.

## 4.5 Relevant Protocol Deviations

In case of any major protocol deviation or violation, the Investigator and Octapharma will decide on the further participation of the patient in this study after having discussed all relevant aspects.

## 4.6 Subsequent Therapy

Not applicable.

## **5** INVESTIGATIONAL MEDICINAL PRODUCT(S)

## 5.1 Characterisation of Investigational Product(s)

*Human-cl rhFVIII* is a B-domain deleted, human cell-line derived recombinant FVIII concentrate for intravenous use and will be provided in single use vials containing a nominal potency of 250, 500, 1000 or 2000 IU each of freeze-dried rFVIII concentrate to be reconstituted in 2.5 mL of WFI.

Several batches of the product will be used in the study.

The final product will be released by the responsible Octapharma Quality Control Department, in accordance with a defined final product specification.

## 5.2 Packaging and Labelling

The open-label study design does not necessitate the blinding of study participants or study site personnel with respect to treatment information. Thus, the IMP will be packed and labelled according to local regulations, together with a pre-filled syringe containing 2.5 mL WFI (which will be transferred to the product vial), 1 disposable syringe (10 mL), 1 vial adapter, 1 butterfly needle and 2 alcohol swabs.

Details regarding master labelling can be found in Appendix 1.

## 5.3 Conditions for Storage and Use

The product has to be stored at 2-8°C protected from light. The product must not be frozen.

The Investigators must ensure that the investigational product is stored under appropriate conditions with restricted access. The Investigators will inform the patients' parent(s)/legal guardian(s) of necessary storage conditions once the patients start home treatment.

## 5.4 Dose and Dosing Schedule

Prophylactic treatment is recommended, but finally, it is the decision of the responsible treating physician whether patients will be treated prophylactically or on-demand. Patients may switch from on-demand to prophylactic treatment, or from prophylactic to on-demand treatment during the course of the study.

## Prophylactic Treatment

1 IU factor VIII per kg body weight raises the plasma factor VIII activity by 1.5 % to 2 %.

In case prophylactic treatment is chosen, the patients will be treated with a recommended dose of 20-50 IU FVIII/kg body weight (BW).

Starting the prophylaxis with the first BE is highly recommended.

The frequency of treatment will mainly depend on the patient's clinical situation. For example, prophylaxis may be initiated with every-other-day injections (in order to keep the FVIII trough level >1%) or with once weekly injections, followed by twice and three times weekly, and every other day treatment. In cases of inadequate response, *Human-cl rhFVIII* administration frequency or dose adjustments can be considered at Investigator's discretion.

## On-demand Treatment

In case of bleeds, the patients can be treated on-demand. The dosage and duration of treatment of spontaneous or traumatic bleeds depend on the location and the extent of bleeding as well as on the clinical situation of the patient. Dosage recommendations are given as follows:

- Minor haemorrhage (superficial muscle or soft tissue and oral bleeds): 20-30 IU FVIII/kg BW to achieve an intended target peak level of about 40% to 60%. Repeat dose every 8-24 hours until BE is resolved.
- Moderate to major haemorrhage (haemorrhage into muscles, into oral cavity; haemarthrosis, known trauma): 30-40 IU FVIII/kg BW to achieve an intended target peak level of about 60% to 80%. Repeat dose every 6-24 hours until BE is resolved.
- Major to life-threatening haemorrhage (intracranial, intra-abdominal, gastro-intestinal or intrathoracic bleeds, central nervous system bleeds, bleeding in retropharyngeal spaces or iliopsoas sheath, eyes/retina, fractures or head trauma): initial dose of 40-60 IU FVIII/kg BW to achieve an intended target peak level of 100% to 120%. Repeat dose of 20-50 IU FVIII/kg BW every 6-12 hours until BE is resolved.

## Surgical Prophylaxis

The dosage and duration of treatment with *Human-cl rhFVIII* will depend on the type of surgery and the patient's individual incremental recovery. Dosage recommendations are given as follows:

- Minor surgeries including tooth extractions: 25-30 IU FVIII/kg BW starting within 3 hours prior to surgery to achieve an intended target peak level of >30%. Repeat one dose every 12-24 hours if needed. Trough levels should be maintained at ≥30%.
- Major surgeries: 40-60 IU FVIII/kg BW within 3 hours prior to surgery to achieve an intended target peak level of approximately 100%. Repeat if necessary after 6-12 hours initially and for at least 6 to 14 days until healing is complete and recurrence to regular prophylactic treatment is possible. Trough levels should be maintained at >50%.

## Recovery Investigation (Optional)

A dose of 40 IU FVIII/kg BW (labelled potency) will be administered on the occasion of the recovery investigations. For the calculation of recovery, the actual potency (measured using both chromogenic (CHR) and one-stage (OS) assays) of *Human-cl rhFVIII* will be used. *In vivo* recovery will be calculated from the FVIII plasma level before infusion and the peak level obtained from the 15 minutes and 1 hour post-infusion samples. Recovery investigations can be done with the first *Human-cl rhFVIII* administration, or within the first three months after treatment start with *Human-cl rhFVIII*, in any case in a non-bleeding patient. They are recommended being controlled every 6 months thereafter.

## Immune Tolerance Induction (ITI) (if applicable)

Patients who develop a clinically significant and non-transient FVIII inhibitor will be offered to start ITI with the IMP. Inhibitors that 'disappear' without any clinical signs or symptoms, where no FVIII dosing increase was required, and that turn to <0.6 BU within a period of 6 months after first detection are regarded as "transient".

The modified Bonn Protocol for inhibitor elimination is recommended:

- Low responders (<5 Bethesda Units [BU]) should receive 50-100 IU FVIII/kg BW daily or every second day. In case the inhibitor increases to 5 BU or more, the patient should switch to the high responder regimen.
- High responders ( $\geq$ 5 BU) should receive 100-150 IU FVIII/kg BW every 12 hours.

Once the inhibitor is eliminated (<0.6 BU), the FVIII recovery is  $\geq$ 66% of normal (defined as 1 IU FVIII/kg BW raises the plasma FVIII activity by 1.5%), and the half-life of FVIII is at least 6 hours, a continuous reduction of about 10% of the initial ITI dosage should be initiated, until the patient has reached a prophylactic treatment regimen of 30-50 IU FVIII/kg BW every other day.

Any other ITI approach using Human-cl rhFVIII as the selected FVIII concentrate is possible.

All treatment details and the further development of the inhibitor titre need to be documented.

Patients who do not start ITI within one year after inhibitor detection are withdrawn from the study.

## 5.5 Preparation and Method of Administration

*Human-cl rhFVIII* will be provided in single use vials containing a nominal potency of 250, 500, 1000 or 2000 IU each of freeze-dried rFVIII concentrate to be reconstituted in 2.5 mL of WFI.

Prior to injection, the solution must have reached room temperature, without taking any specific warming-up measures. The preparation should be administered within 3 hours after reconstitution at one single occasion. The solution is a clear or slightly opalescent colourless solution. Solutions that are cloudy or have deposits must not be used. *Human-cl rhFVIII* should be injected intravenously by bolus injection (maximally 4 mL/minute) by using aseptic technique.

## 5.6 Blinding, Emergency Envelopes and Breaking the Study Blind

Not applicable.

## 5.7 Treatment Compliance

## 5.7.1 Drug Dispensing and Accountability

A drug dispensing log will be kept up to date by the Investigator, detailing the dates, batch numbers, and quantities of investigational product dispensed to each patient. The inventory will be available to the Study Monitor in order to verify drug accountability in the course of the study. Patients' parent(s)/legal guardian(s) will be advised to return any empty vials and unused investigational product on the occasion of the study visits.

Any unused investigational product not dispensed, or returned by the patient, will be counted and returned to the Sponsor. In certain cases, unused supplies might have to be destroyed at the study site. However, this is only applicable after drug accountability has been verified and fully re-conciliated, and after written approval from the Sponsor has been obtained.

The Investigator will ensure that such a disposition does not expose patients to risks linked to the investigational product. The Investigator and the Sponsor will maintain records of any such alternate disposition to permit accurate drug accountability.

## 5.7.2 Assessment of Treatment Compliance

Patients will usually undergo at-home treatment (treatment will likely be administered by parents/guardians due to the expected young age of the patients or by general practitioners or nurses). At the first visit, the Investigator will provide them with a sufficient amount of trial medication (in cooling boxes, if appropriate) and a diary. The Investigator will advise the parents/guardians on how to fill in the diary. The diary will include detailed written instructions for all assessments to be made. Furthermore, the efficacy rating criteria and the criteria for assessing the severity of a bleed will be explained. The Investigator will emphasise the necessity of a careful documentation of all treatment details. The recording of at-home injections will include the date and time, dose, batch number, and reason for injection (i.e. prophylaxis, BE treatment). IMP is provided with tear-off labels that must be placed in the diary.

In case of treatment of BEs, the patient's parents/guardians will document the site and severity of the bleed, the start and end dates and time, and carry out an efficacy assessment according to the explanation provided in the diary.

Study product administrations that are overseen by the Investigator (e.g. treatment in relation to the recovery investigations or in case of severe BEs treated at the study site), are to be documented in the patient's journal (by the Investigator), as well as in the patient's diary (by the parents/guardians).

In addition, the patient's parents/guardians will record any concomitant medications taken during the study period in their diaries.

For each follow-up visit at the study site, the parents/guardians must bring all diaries to be reviewed and validated by site personnel.

## **6 STUDY CONDUCT**

## 6.1 Observations by Visit

## 6.1.1 Screening (Visit 1)

Parents/legal guardians have to be informed about the study details and have to give their written informed consent before any investigations and assessments can be performed. The following will be documented/assessed:

- Check of inclusion- and exclusion criteria
- Demographics, including patient's blood type and FVIII inhibitor risk factors
- Medical history
- Vital signs
- Height
- Body weight
- Physical examination
- Safety laboratory parameters
- FVIII:C (CHR and OS assay)
- FVIII inhibitor screen
- FVIII gene mutation analysis (mandatory, can be performed later during the study)
- Immunogenotyping (HLA-typing, immune response gene expression), (optional)
- RNA expression analysis (optional)

- *In vitro* immunogenicity of FVIII products (optional)
- Epitope mapping: optional, available pre-treatment samples will be analysed from study patients who later on developed an inhibitor to FVIII and started ITI. In addition, samples available from an inhibitor negative control group will be tested: already available plasma samples from ~20 PUPs included into the study in Ukraine and Moldova, which were drawn prior to the first exposure to FVIII are planned to be analysed in retrospect.

The Investigator will hand out the patient diary and instruct the parent(s)/legal guardian(s) on how to document details of treatment with *Human-cl rhFVIII*, bleeds, AEs and concomitant medication. The parent(s)/legal guardian(s) will receive a sufficient amount of study product for home treatment (in cooling boxes, if appropriate) and will be instructed on how to store and administer it.

Immunogenotyping is suggested to be performed at screening; however, it can be performed at any point during the study. It is suggested that the sampling coincides with regular study visits whenever possible.

# 6.1.2 **Procedures During the Follow-Up Part of the Study**

# Follow-Up Visits (until ED 20):

The patients will visit the study site every 3-4 EDs until 20 EDs have been reached. At these visits, blood samples will be obtained for FVIII inhibitor screen and optionally RNA expression analysis (after a wash-out period of at least 2, preferably 3 days after the previous IMP administration). Samples are analysed in the central laboratories.

At these visits, the patient diary will be reviewed (any IMP injection, any bleed) in order to transfer data into the CRF. The occurrence of AEs and changes in weight and concomitant medication will be checked and documented.

# Follow-Up Visits (after ED 20 until ED 100):

After ED 20 has been reached, patients will visit the study site every 10-12 EDs. At these visits, blood samples will be obtained for FVIII inhibitor screen (after a wash-out period of at least 2, preferably 3 days after the previous IMP administration).

At these visits, the patient diary will be reviewed (any IMP injection, any bleed) in order to transfer data into the CRF. The occurrence of AEs and changes in concomitant medication will be checked and documented. Samples are analysed in the central laboratory.

# Follow-Up Visits (every 3 months $\pm$ 2 weeks):

If appropriate, the above-described follow-up visits may be combined with regular 3-monthly follow-up visits ( $\pm 2$  weeks), stipulating some supplementary investigations are performed: the safety laboratory parameters will be assessed (samples are analysed locally) and vital signs will be measured pre- and – in case IMP was injected – 30-60 minutes post-injection and the patient's BW will be measured.

Once every 6 months a physical examination is performed.

If the optional recovery investigation is done, it is recommended that it will be performed with the first *Human-cl rhFVIII* administration, or within the first three months after treatment start and every 6 months thereafter, in any case in a non-bleeding patient.

Recovery visits should be timed so that they coincide with other study visits whenever possible. The *in vivo* recovery will be calculated from the FVIII plasma levels before infusion and the peak level obtained from the 15 minutes and 1 hour post-infusion samples. Samples are analysed in the central laboratory.

In case the patient did not require any IMP from screening until the 3-Monthly Follow-Up visits during the first year, the blood sampling (inhibitor screen, safely laboratory) after 3 and 9 months is optional. After 6 and 12 months a sample is mandatory.

## Additional Health Economic Evaluation:

Parents / Caregivers will be asked to fill out a short questionnaire as part of the patient diary that asks about their time commitments, and productivity loss.

These questions should be answered by both parents (if applicable) on a quarterly basis, finally covering the entire study period.

- Do you currently hold a paid job?
- Did your child's Haemophilia A oblige you to be off work at any time in the past three months?
- Did other people take over and perform your usual household tasks in the past three months in connection with your child's Haemophilia A?
- How much of the time you cared for your child in the past 3 months was specifically related to Haemophilia A? *Consider time related to product administration, receiving education on home treatment, time related to hospital visit, physicians visits etc.*

# ITI Patient Follow-Up:

Patients developing an inhibitor and not starting ITI will be withdrawn from the study, once it can be ruled out that the inhibitor is transient / not requiring ITI. Inhibitors that `disappear' without any clinical signs or symptoms, where no FVIII dosing increase was required, and that turn to <0.6 BU within a period of 6 months after first detection are regarded as "transient".

Patients developing an inhibitor and starting ITI will be closely monitored. Depending on the development of the inhibitor level: a bi-weekly (later on monthly to 3-monthly) inhibitor titre testing is considered appropriate. Optional epitope mapping can be performed once the inhibitor is detected (pre-ITI start), as close as possible after the peak inhibitor level, and after inhibitor eradication. These patients' epitope mapping samples optionally taken at screening / prior to the first exposure to FVIII will also be analysed. Optional RNA expression analysis can be performed alongside the inhibitor testing at initiation of ITI, 2 and 4 weeks after ITI initiation, and then on a monthly basis until Month 6. This may give information on motifs that predict success that should be evident in the first 6 months and give mechanistic information on immune-tolerance.

Once the inhibitor is eliminated, a normalised recovery and half-life are expected during the continued ITI. Patient observation visits including inhibitor screen and FVIII measurements are recommended according to progress of the ITI. Samples to test the recovery are recommended to be drawn at baseline and 15 minutes post-injection. For the half-life evaluation, the following sampling time points are recommended: baseline, 15 minutes, 3, 6, 9, 12, 24 hours post-injection. No wash-out period needs to be respected prior to blood sampling; no ITI injection should be skipped prior to or during the half-life evaluation (last blood sampling should be performed before the next regular ITI dose is injected).

Patients will complete study participation after a complete success of the ITI (inhibitor-free, normalised recovery and half-life), and the start of regular prophylactic treatment, or after a maximum ITI period of 36 months.

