- Minor surgeries including tooth extractions: 25-30 IU FVIII/kg BW starting within 3 hours prior to surgery to achieve an intended target peak level of >30%. Repeat one dose every 12-24 hours if needed. Trough levels should be maintained at  $\ge 30\%$ .
- Major surgeries: 40-60 IU FVIII/kg BW within 3 hours prior to surgery to achieve an intended target peak level of approximately 100%. Repeat if necessary after 6-12 hours initially and for at least 6 to 14 days until healing is complete and recurrence to regular prophylactic treatment is possible. Trough levels should be maintained at > 50%.

Recovery investigation (optional):

Patients will receive 40 IU FVIII/kg BW for *in vivo* recovery evaluation. Blood samples are taken at baseline, 15 minutes and 1 hour after the IMP administration.

Immune tolerance induction (ITI) (if applicable):

Patients who develop a clinically significant and non-transient inhibitor will be offered to start ITI with the Investigational Medical Product (IMP).

The modified Bonn Protocol for inhibitor elimination is recommended:

- Low responders (<5 Bethesda Units [BU]) should receive 50-100 IU FVIII/kg BW daily or every second day. In case the inhibitor increases to 5 BU or more, the patient should switch to the high responder regimen.
- High responders ( $\geq$ 5 BU) should receive 100-150 IU FVIII/kg BW every 12 hours. Once the inhibitor is eliminated (<0.6 BU), the FVIII recovery is  $\geq$ 66% of normal, and the half-life of FVIII is at least 6 hours, a continuous reduction of about 10% of the initial ITI dosage should be initiated, until the patient has reached a prophylactic treatment regimen of 30-50 IU FVIII/kg BW every other day.

Any other ITI approach is possible.

All treatment details, including the needs of bypassing agents, and the further development of the inhibitor titre need to be documented.

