In case the patient did not require any IMP from screening until the 3-Monthly Follow-Up visits during the first year, the blood sampling (inhibitor screen, safely laboratory) after 3 and 9 months is optional. After 6 and 12 months a sample is mandatory.

ITI Patient Follow-Up:

Patients who develop an - non-transient - inhibitor and do not agree to start an ITI will be withdrawn from the study.

Patients developing an inhibitor and starting ITI will be closely monitored, once their parents / legal guardians have been informed about the ITI treatment details and gave their written consent before ITI initiation. Depending on the development of the inhibitor: a bi-weekly (later on monthly to 3-monthly) inhibitor titre testing is considered appropriate.

Optional epitope mapping can be performed once the inhibitor is detected.

*Optional* RNA expression analysis can be performed alongside the inhibitor testing at initiation of ITI, 2 and 4 weeks after ITI initiation, and then on a monthly basis until month 6. This may give information on motifs predicting success that should be evident in the first 6 months and give mechanistic information on immune-tolerance.

Once the inhibitor is eliminated, a normalised recovery and half-life are expected during the continued ITI. Patient observation including testing visits is recommended according to progress of the ITI. Samples to test the recovery are recommended to be drawn at baseline and 15 minutes post-injection. For the half-life evaluation, the following sampling time points are recommended: baseline, 15 minutes, 3, 6, 9, 12, (24) hours post-injection.

Patients will complete study participation after a complete success of the ITI (inhibitor-free, normalised recovery and half-life), or after a maximum ITI period of 36 months.

Surgical Visits:

Study subjects may undergo surgical interventions during the course of the study. Depending on the type of surgery, subjects may be hospitalised or not (in case of certain minor surgeries with low risk of post-operative bleeding) at the discretion of the Investigator. Details of surgery, *Human-cl rhFVIII* dosing, expected and actual blood loss, concomitant treatment (including need for additional blood transfusions), and lab investigations will be documented, as well as details of hospitalisation (start and end date, regular ward, intensive care unit stay).

Completion Visit:

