## Completion Visit:

For each patient, the study is completed once 100 EDs have been reached, or after a maximum of 5 years study participation - from screening.

Patients undergoing an ITI complete the study after a successful elimination of the inhibitor ("complete success" criteria see above), but after a maximum ITI period of 36 months.

At this visit, blood samples will be obtained for FVIII inhibitor screen (after a wash-out period of at least 2, preferably 3 days after the previous IMP administration) and the safety panel. Samples for FVIII inhibitor screen are analysed in the central laboratory.

The vital signs and a physical examination will be performed. The patient's BW will be measured. The occurrence of AEs and changes in concomitant medication are checked and documented.

At this visit, the patient diary will be reviewed (any IMP injection, any bleed) in order to transfer data into the CRF.

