10.1 Complete success of ITI therapy

Complete success of a patient’s ITI will be defined as:

- FVIII:C inhibitor negative (<0.6 BU) (at two sequential measurements)
- Recovery ≥ 0.99 %/(IU/kg BW) (= 66% of 1.5 % (IU/kg BW))
- terminal half-life ≥ 6 hours

Complete success is

- 1) documented in the “ITI Study Completion” by the investigator and
- 2) derived from the documented data on the objective criteria
 - in the inhibitor data
 - as derived from the recovery/half-life data
(central and/or local lab determinations with one-stage assay and/or chromogenic assay)

If more than one lab determination is available (e.g. local and central lab; several assays), worst available values are taken into account for the inhibitor criterion (highest titre) and the recovery criterion (lowest IVR); this also applies for the half-life criterion (lowest half-life). However, there may be exceptions when there is a difference in available data for PK analysis and one of the series of measurements is expected to provide more reliable estimations of the terminal half-life data than the other(s); if necessary, reliability of series of measurements in terms of available data for PK analysis will be assessed in data review meetings before interim and final analysis.

11 **EVALUATION OF SAFETY PARAMETERS**

11.1 **Adverse Events**

All adverse events occurring or worsening after initiation of study treatments until the completion visit (treatment emergent AEs) will be displayed in summary tables and listings.

Incidences of adverse events will be given as numbers and percentages of subjects; for AEs judged to be related to study drug or occurring during or within 24 hours of the end of an infusion also the numbers and percentages of infusions associated with such AEs will be presented:

- Any AE (by MedDRA (version 15.0 or later) preferred term (descending frequency) and by MedDRA System Organ Class (SOC))
- Any serious AE (by MedDRA System Organ Class (SOC)/ preferred term)
- Any AE probably or possibly related to the trial drug (by MedDRA System Organ Class (SOC)/ preferred term)
- Any AE temporally related (within 24 hours after end of infusion*) to the trial drug (by MedDRA preferred term (descending frequency) and by MedDRA System Organ Class (SOC))
- Any severe AE (by MedDRA System Organ Class (SOC)/ preferred term)
- Any withdrawal due to AE (Adverse drop-out)

* In case another infusion starts within the 24 hours the AE will be related to the last infusion.

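### The protocol's rules for when ITI patients leave the study conflict, and the SAP's complete success can be reached before any dose reduction

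*Protocol*

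**What the plan says.** The protocol states the end of participation for an ITI patient in five places, each with the 36-month maximum as the alternative:

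- Study Outline, ITI Patient Follow-Up: "Patients will complete study participation after a complete success of the ITI (inhibitor-free, normalised recovery and half-life), or after a maximum ITI period". Prophylaxis is not mentioned.
- Study Outline, Completion Visit: "Patients undergoing an ITI complete the study after a successful elimination of the inhibitor". Recovery, half-life and prophylaxis are not mentioned.
- Section 6.1.2, ITI Patient Follow-Up: "Patients will complete study participation after a complete success of the ITI (inhibitor-free, normalised recovery and half-life), and the start of regular prophylactic treatment". This is the only place that names prophylaxis.
- Section 6.1.2, Completion Visit: the elimination wording again, with a reference back to the complete-success criteria. Prophylaxis is not repeated.
- Section 6.2.1: a successful ITI, not defined there.

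Section 5.4 and the Study Outline use three findings as the signal to begin lowering the dose: inhibitor below 0.6 BU, recovery at least 66% of normal, and half-life at least 6 hours. Then "a continuous reduction of about 10% of the initial ITI dosage should be initiated, until the patient has reached a prophylactic treatment regimen"; the target is 30-50 IU/kg every other day. Normal recovery means that "1 IU FVIII/kg BW raises the plasma FVIII activity by 1.5" per cent.

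SAP 10.1 defines complete success by three criteria. The first is "FVIII:C inhibitor negative (<0.6 BU) (at two sequential measurements"); the others are recovery of at least 0.99 % per IU/kg and a terminal half-life of at least 6 hours. Success is both documented by the investigator on the ITI Study Completion form and derived from the data. SAP 9.6 reports the percentage with complete success and a Kaplan-Meier curve of the time to it.

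**The concern.** The thresholds that start the taper in section 5.4 are the ones that end participation in the Study Outline's ITI paragraph. Section 6.1.2 adds the start of regular prophylaxis which, under section 5.4, lies at the far end of the taper. Two sites can each follow the protocol and release comparable patients at opposite ends of the dose reduction.

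Two things are at stake. The first is observation: an inhibitor that returns while the dose is being lowered would be seen at one site and could be missed at the other. The second is meaning: a reader of the study report may take complete success to mean that tolerance held on ordinary dosing, and the definition does not require that.

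**Working it through.** **1. Are the SAP success thresholds the same as the taper trigger?**

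- Recovery: 66% of 1.5 = 0.66 × 1.5 = 0.99 % per IU/kg. This reproduces the SAP figure.
- Half-life: at least 6 hours in both.
- Inhibitor: below 0.6 BU in both. The SAP adds a second sequential negative measurement and sets no interval between the two.

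All three cut-offs match. Neither SAP 9.6 nor SAP 10.1 has a condition on dose, taper or prophylaxis.

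**2. How large is the taper?** Inputs are the section 5.4 doses, as average IU/kg per day. Steps = (1 − end/start) ÷ 0.10, rounded up, because the reduction is about 10% of the initial dosage.

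- End of taper: 30-50 every other day = 15-25 per day.
- High responders: 100-150 every 12 hours = 200-300 per day. The ratio runs from 200/25 = 8 to 300/15 = 20. Steps: (1 − 25/200)/0.10 = 8.75, so 9; (1 − 15/300)/0.10 = 9.5, so 10.
- Low responders: 50-100 daily or every second day = 25-100 per day. From 25 to 25 there are 0 steps; from 100 to 15, (1 − 15/100)/0.10 = 8.5, so 9.

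The documents give no time per step, so the calendar length of the taper cannot be computed.

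**3. Which outputs depend on the exit rule?**

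- The derived success status and date (Tables 14.2.12 and 14.2.13, Figure 14.2.14) rest on SAP 10.1. Adding the prophylaxis condition to the exit rule changes neither.
- The investigator's ITI Study Completion entry is made at exit, so it can depend on the rule the site applied.
- ITI exposure and consumption (14.2.7 to 14.2.9), final-assessment outputs (14.2.54, 14.2.55.2, 14.2.56.2) and adverse events during ITI (14.3.1.16, 14.3.1.17) depend on how long the patient is followed.

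**4. What happens if the inhibitor returns during the taper?** SAP 9.6 and 10.1 are silent. SAP 3.4.1 closes the inhibitor period at the first confirmed fall below 0.6 BU and does not say what would reopen it.

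**5. Does the completion visit fit?** Section 6.1.2 asks for a wash-out of at least two days before the completion inhibitor sample. On every-other-day dosing this omits nothing. On 12-hourly dosing it omits the doses at 12, 24 and 36 hours. The ITI paragraph of the same section says that no wash-out is needed and that ITI injections are not to be missed around the half-life evaluation. The two statements concern different samples, but they sit uneasily together for a patient who leaves on full ITI dosing.

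**The case against.** The strongest reply is that the SAP applies one definition of success to every patient, whatever the exit date, and asks for two sequential negatives. That stands. A reader might infer that the success rate is inflated, or that Figure 14.2.14 mixes patients who met the criteria at full dose with patients who kept tolerance after tapering. The documents do not support this. The derived event is the same whether or not the patient is kept until prophylaxis, and no relapse rate is given from which an inflation could be computed.

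Other points also hold in part:

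- The Completion Visit text of section 6.1.2 refers back to the complete-success criteria, which softens the conflict within that section. It does not reach the Study Outline or section 6.2.1.
- The regimen is only recommended, other ITI approaches with the product are allowed, and some low responders may have no taper. Leaving at full dose is therefore possible, not inevitable.
- ITI success is not among the listed objectives and is reported descriptively.
- Section 5.4 requires treatment details and titres to be documented, and the SAP lists ITI doses (16.2.5.6) and inhibitor results (16.2.8.2). A taper within the study can be traced; one after exit cannot.

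Counting a return of the inhibitor as loss of success would be a new endpoint. The inconsistency does not require it.

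**Conclusion.** The concern holds as a conflict between exit rules and a limit on what complete success can show. Where the recommended regimen is used, compliant sites can release patients before or after a taper of 9 to 10 steps in high responders (an 8- to 20-fold reduction) and 0 to 9 steps in low responders. The step counts assume that the 10% applies to the average daily dose.

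The derived success status and date are not biased by this difference. They describe criteria that can be met before any dose reduction, and they say nothing about tolerance afterwards. A return of the inhibitor during the taper has no stated effect and, under the Study Outline's rule, may go unobserved. The ITI consumption, final-assessment and adverse-event outputs and the investigator's completion entry can differ by exit rule, by an amount the documents do not allow one to calculate. The primary endpoint is not affected. Which exit rule is right is for the sponsor to decide.

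**What to change.** **Protocol.** Reconcile the Study Outline (ITI Patient Follow-Up and Completion Visit) with sections 5.4, 6.1.2 (both paragraphs) and 6.2.1 so that there is one completion rule for ITI patients. State whether the taper falls within study participation and within the 36-month limit. Reconcile the completion-visit wash-out with the ITI paragraph of section 6.1.2.

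**SAP.** Keep the SAP 10.1 definition of complete success. Add to Table 14.2.12 a descriptive row that gives, among complete successes:

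- the ITI regimen at the time the criteria were met;
- the inhibitor status at the last test after dose reduction or on regular prophylaxis: negative, returned to 0.6 BU or more, or not observed.

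The row can be built from data already listed in 16.2.5.6 and 16.2.8.2.

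**Cost.** A protocol clarification, slightly more analysis work and, depending on the rule the sponsor chooses, a different length of follow-up for some ITI patients. If that rule lengthens exposure to the product, section 10.4 requires ethics committee approval.
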